4.4.6. Biomarker Analyses

The effect of GSK3228836 and PegIFN sequential therapy on immunological biomarkers will be assessed. The relationship(s) between virology biomarkers including HBsAg and immunological biomarkers will be described. Details of the immunology endpoints will be included in a separate biomarker analysis plan.

4.5. Safety Analyses

All safety analyses will be based on the Safety population.

Exposure to study medication, measured by the number of injections and proportion of planned number of injections of study drug, will be summarised by treatment arm.

4.5.1. Extent of Exposure

Extent of exposure will be summarized by presenting number of participants in various exposure duration categories, overall duration of exposure, and study intervention compliance.

Number of days of exposure to study drug will be calculated separately for GSK3228836 and PegIFN based on the formula:

- $\text{Duration of Exposure in Days} = \text{Last injection date} - \text{First injection date} + 1$

The duration of exposure in weeks will be calculated as duration of exposure in days divided by 7.

The cumulative actual dose will be calculated separately for GSK3228836 and PegIFN based on the formula:

- $\text{Cumulative Actual Dose} = \text{Sum of Dose administered during GSK3228836 or PegIFN dosing period}$

The dose intensity (mg/wk) will be calculated separately for GSK3228836 and PegIFN based on the formula:

- $\text{Dose Intensity} = \text{Cumulative Actual Dose} / \text{Total Actual Number of Weeks of Dose administration}$

The cumulative injected volume will be calculated separately for GSK3228836 and PegIFN based on the formula:

- $\text{Cumulative Injected Volume} = \text{Sum of Injected Volume during GSK3228836 or PegIFN dosing period}$

The weekly injected volume (mL/wk) will be calculated separately for GSK3228836 and PegIFN based on the formula:

- $\text{Weekly Injected Volume} = \text{Cumulative Injected Volume} / \text{Total Actual Number of Weeks of Dose administration}$

4.5.2. Adverse Events

All AE summaries will be based on treatment emergent events unless otherwise specified. An adverse event (AE) is considered treatment emergent if the AE onset date is on or after treatment start date. If AE start date is completely missing and the end date is on or after the treatment start date, the AE will be assumed to be treatment emergent. AEs with onset date on or after start date of treatment with GSK3228836 will be classified as occurring during the GSK3228836 treatment period, and AEs with onset date on or after start date of treatment with PegIFN will be classified as occurring during the PegIFN treatment period. AEs starting after end of GSK3228836 treatment period and prior to PegIFN treatment start will be considered as AEs occurring during PegIFN eligibility period.

Adverse events will be coded using the latest version of Medical Dictionary for Regulatory Authorities (MedDRA) coding dictionary, to give a preferred term and a system organ class. These preferred terms and system organ classes will be used when summarizing the data.

The severity of AEs and SAEs will be determined by the investigator according to the 'Division of Acquired Immune Deficiency Syndrome (DAIDS) Table for Grading the Severity of Adult and Pediatric Adverse Events (2017)', unless specified otherwise in the protocol. For AEs by maximum determined grade summary tables, for AEs occurred more than once, the most severe intensity will be included in summaries. Relationship to study treatment, as indicated by the investigator, is classified as not related or related to GSK322836, PegIFN, or both. Adverse events with a missing relationship to study treatment will be regarded as related to the ongoing study treatment or the last study treatment if no treatment is received at the time of AEs.

The following AE summaries will be presented overall and by treatment arm:

1. AEs overview: summarize the number and percentage of participants with any adverse event, AEs related to study treatment, AEs leading to permanent discontinuation of study treatment, withdrawal from the study, any serious adverse events (SAE), SAEs related to study treatment, fatal SAEs and fatal SAEs related to study treatment.
2. All AEs by system organ class (SOC) and preferred term (PT)
3. All AEs by SOC and PT and maximum grade
4. All drug-related AEs by SOC and PT
5. All drug-related AEs by SOC and PT and maximum grade
6. Serious AEs (SAEs) by SOC and PT
7. Serious AEs (SAEs) by SOC and PT and maximum grade
8. Serious Adverse Events by system organ class and preferred term (number of participants and occurrences)
9. AEs leading to withdrawal from the study by SOC and PT
10. AEs leading to withdrawal from the study by SOC and PT and maximum grade
11. AEs leading to permanent discontinuation of study treatment by SOC and PT
12. AEs leading to permanent discontinuation of study treatment by SOC and PT and maximum grade
13. Serious fatal and non-fatal drug/related AEs by SOC and PT
14. AEs by overall frequency
15. Non-serious AEs by SOC and PT (number of participants and occurrences)
16. Non-Serious drug-related adverse events by overall frequency

The above listed summaries will also be presented separately for events occurring during treatment with GSK3228836 and PegIFN, overall and by treatment arm within each treatment period. Drug-related AEs will be summarised for the two treatment periods as follows:

1. Summary of GSK3228836 drug-related adverse events by system organ class and preferred term
2. Summary of GSK3228836 drug-related adverse events by system organ class and preferred term and maximum grade
3. Summary of PegIFN drug-related adverse events by system organ class and preferred term
4. Summary of PegIFN drug-related adverse events by system organ class and preferred term and maximum grade

Number of participants with AEs will be summarized if it is not specified otherwise.

In summary tables where AEs are presented by SOC, PT, and maximum grade, SOC's will be sorted in descending order of the total incidence then alphabetically, PT's will be sorted in descending order of the total incidence then alphabetically within the SOC.

For completely missing or partial missing AE start date or end date, imputation rules will be applied following rules stated in the Output and Programming Specifications (OPS).

Deaths will be listed including primary cause of death.

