Ocular exam (unless completed within 3 months)	X
12-lead ECG	X
Neuropsychiatric assessment (C-SSRS and BDI-II)	X
LABORATORY ASSESSMENTS	
Serum hCG pregnancy test (women of childbearing potential [WOCBP])	X
FSH/Estradiol (to confirm status of women of non-child-bearing potential) ¹	X
Haematology/Chemistry/Urinalysis	X
TSH, T4	X
Urine ACR	X
PT, INR, aPTT	X
HIV, hepatitis D, and hepatitis C screen	X
Hepatitis B profile (HBsAg, HBV DNA, HBeAg)	X
Alpha-fetoprotein	X
APRI/ FibroSure	X
ANCA (with MPO-ANCA, PR3-ANCA if results are positive or border-line positive)	X
Complement C3, C4, C5a, hsCRP, MCP-1, complement Bb, Ang-2	X

1. As appropriate to confirm menopause

Table 2 GSK3228836 Treatment Period: Treatment Arm 1 (Week 1-24)

Day	1	4	8	11	15	22	29	36	43	50	57	64	71	78	85	92	99	106	113	120	127	134	141	148	155	162			
Week	1	1	2	2	3	4	5	6	7	8	9	10	11	12	13	14	15	16	17	18	19	20	21	22	23	24			
Window (days)		±1 day			±2	±3 days																							
Randomisation	X																												
GSK3228836 dosing	X	X	X	X	X	X	X	X	X	X	X	X	X	X	X	X	X	X	X	X	X	X	X	X	X	X	X		
Safety Assessments																													
AE/SAE review	X	X	X	X	X	X	X	X	X	X	X	X	X	X	X	X	X	X	X	X	X	X	X	X	X	X	X		
Conmed review	X	X	X	X	X	X	X	X	X	X	X	X	X	X	X	X	X	X	X	X	X	X	X	X	X	X	X		
Symptom directed exam	X						X				X				X				X				X						
Vital signs	X	X	X	X	X	X	X	X	X	X	X	X	X	X	X	X	X	X	X	X	X	X	X	X	X	X	X		
12 lead ECG																									X ⁴	X ⁴			
Injection site reactions	X	X	X	X	X	X	X	X	X	X	X	X	X	X	X	X	X	X	X	X	X	X	X	X	X	X	X		
Laboratory Assessments																													
Pregnancy test (WOCBP)	X ¹						X				X				X				X					X					
Haematology [includes platelet and WBC with differential]	X		X		X	X	X	X	X	X	X	X	X	X	X	X	X	X	X	X	X	X	X	X	X	X	X		
PT, INR, aPTT	X						X				X				X				X					X					
TSH, T4																										X			
Chemistry	X		X		X	X	X	X	X	X	X	X	X	X	X	X	X	X	X	X	X	X	X	X	X	X	X		
Urinalysis	X		X		X	X	X	X	X	X	X	X	X	X	X	X	X	X	X	X	X	X	X	X	X	X	X		
Urine ACR	X				X		X		X		X		X		X		X		X		X		X		X	X			
HBsAg and HBV DNA	X		X		X	X	X	X	X	X	X	X	X	X	X	X	X	X	X	X	X	X	X	X	X	X	X		
Anti- HBsAg and anti-HBeAg	X						X				X				X				X					X					
HBeAg ³	X		X		X	X	X	X	X	X	X	X	X	X	X	X	X	X	X	X	X	X	X	X	X	X	X		
Complement C3, C4, C5a, Bb, hs-CRP, MCP-1	X				X		X		X		X		X		X		X		X		X		X		X				
ANCA, Ang II	X						X				X				X				X					X					
PK GSK3228836	X	X	X	X				X						X							X					X			
HBV RNA, and Sequencing (HBV genotype/phenotype; HBV DNA and/or RNA)	X				X		X		X		X		X		X		X		X		X		X		X				

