1.2. Study Design

Overview of Study Design and Key Features	

The diagram illustrates the study design for two treatment arms, each with N=50 participants. Both arms start with 'Continuation of Nucleos(t)ide Therapy' from Week 0 to Week 72. Arm 1 receives 'GSK-836 - 24 Wks' from Week 0 to Week 24, followed by 'PEG-IFN' from Week 24 to Week 48, and 'OFF TREATMENT' from Week 48 to Week 72. Arm 2 receives 'GSK-836 - 12 Wks' from Week 0 to Week 12, followed by 'PEG-IFN' from Week 12 to Week 48, and 'OFF TREATMENT' from Week 48 to Week 72. A legend indicates that the dotted area represents Peg-IFN treatment initiation only after patient eligibility is confirmed, and a star marks the primary endpoint at 24 weeks off-treatment.
	
Design Features	
 Phase IIb, multi-center, randomised, open label study to assess the efficacy and safety of sequential treatment with GSK3228836 followed by Pegylated Interferon Alpha 2a in participants with CHB while on stable nucleos(t)ide treatment.
Study Intervention	
 Arm 1: 300 mg GSK3228836 once/week for 24 weeks (plus loading doses of 300 mg GSK3228836 on Day 4 and Day 11) followed by PegIFN (180 mcg/week for up to 24 weeks). Arm 2: 300 mg GSK3228836 once/week for 12 weeks (plus loading doses of 300 mg GSK3228836 on Day 4 and Day 11) followed by PegIFN (180 mcg/week for up to 24 weeks).
Study Intervention Assignment	
 Participants will be randomised in a 1:1 ratio to receive study intervention. Approximately 100 participants are planned to be enrolled in the study. The study team may enrol additional participants to within 10% of the planned 100.
Interim Analyses	
 Administrative Interim analyses: interim analyses to support internal decision making at multiple timepoints throughout the study. Planned efficacy Interim analysis: all participants complete the end-of-treatment visit and a sufficient number of participants complete off-treatment follow-up in order to assess the probability of C2P3. Independent Data Monitoring Committee (IDMC) safety review: approximately every 3 months.

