Summary of post-baseline hepatobiliary laboratory abnormalities will be provided.

The worst-case urinalysis results post-baseline (on-treatment and off-treatment periods combined) relative to baseline will be summarized.

Summaries of result shifts from baseline, worst-case results post-baseline relative to baseline, and results with increase to \geq maximum toxicity grade post-baseline for chemistry, haematology, urinalysis, and immunology as applicable, will also be presented for treatment with GSK3228836 and PegIFN separately, by treatment arm and in total within each treatment period.

GSK3228836 liver chemistry monitoring and stopping event reporting will be summarized and listed. The liver monitoring and stopping criteria are described in the protocol Section 7.1.1.

GSK3228836 haematological monitoring and stopping events will be summarized and listed based on laboratory parameters (platelet count and anti-platelet antibodies). The haematological stopping criteria are described in the protocol Section 7.1.2.

GSK3228836 drug induced kidney injury (renal) monitoring and hold or stopping events will be identified programmatically and will be summarized and listed based on laboratory parameters (ACR, urinalysis red blood cells (RBC), serum creatinine, and eGFR). The kidney injury monitoring and stopping criteria are described in the protocol Section 7.1.3.

Drug induced vascular injury and complement monitoring/stopping event will be summarized and listed based on laboratory parameters (C3, C4, Bb, C5a, hs-CRP, MCP-1, p-ANCA, c-ANCA, eGFR, bilirubin, and platelet count). The drug induced vascular injury and complement monitoring and hold/stopping criteria are described in the protocol Section 7.1.4.

Hold/stopping event profile for GSK3228836 will be provided for any subject who has met hold or stopping criteria specified in protocol Section 7.1. Relevant information will be reported, including baseline characteristics, AEs/SAEs, concomitant medication, medical history/current medical conditions, study treatment administration details, laboratory values, and individual line plots of complement (C3/C4/C5a/Bb), inflammatory markers (hs-CRP/MCP-1), serum creatinine/creatinine clearance or eGFR/ACR, and platelet count.

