6.1.5. Study Intervention Compliance

A summary of overall compliance for GSK3228836 and PegIFN based on the exposure data will be produced. Overall compliance will be summarized using descriptive statistics as well as the categories <80%, 80%-100%, and >100%.

Compliance will be summarized both in terms of number of injections administered and total dose received during the planned on-treatment period.

Percentage of compliance will be calculated as follows:

$$\text{Study intervention Compliance (\%)} = (\text{Number of actual doses}^{[1]} / \text{Number of planned doses}) * 100$$

$$\text{Study dose Compliance (\%)} = (\text{Total Cumulative Actual Dose}^{[2]} / \text{Total Cumulative Planned Dose}) * 100$$

- 1) GSK3228836 :- The planned number of doses are 26 or 14 for Arm 1 & Arm 2 respectively. The Planned Total Cumulative Dose is calculated by multiplying number of planned doses and dose that is, 300 mg.

$$\text{Planned Total Cumulative Dose} = \text{Number of planned doses} * 300 \text{ mg}$$

- 2) PegIFN: - The planned number of doses are 24 if subject becomes eligible for PegIFN Week 1. If subject becomes eligible after PegIFN Week 1, then follow Protocol table 6 to identify number of planned doses –

Table 6 PegIFN Dosing for Participants becoming Eligible for PegIFN after Week 1

Become Eligible for PegIFN at PegIFN Eligibility Week (Table 5)	PegIFN Dosing (Table 4) should continue until PegIFN Dosing Week
2	23
3	22
4	21
6	19
8	17
10	15
13	12

The Planned Total Cumulative Dose is calculated by multiplying number of planned doses and dose that is, 180 mcg.

$$\text{Planned Total Cumulative Dose} = \text{Number of planned doses} * 180 \text{ mcg}$$

[1] : Subject might receive reduced dose that is smaller than the number of injections. Reduced dose should be still counted as ‘one’ dose for *Number of actual doses* calculations.

[2] : Refer to SAP Section 4.5.1

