6.2.2. Study Phase and Period

Safety assessments and events will be classified according to the time of occurrence relative to the study intervention period.

Table 13 Study Phase Definitions

Study Intervention Phase	Definition
Pre-Treatment	For Assessments – Date ¹ ≤ Study Treatment Start Date For Events – Date ¹ < Study Treatment Start Date
On-Treatment	For Assessments – Study Treatment Start Date < Date ¹ < Last Treatment Stop Date + 7 days For Events – Study Treatment Start Date ≤ Date ¹ < Last Treatment Stop Date + 7 days
Post-Treatment	Date ¹ ≥ Last Treatment Stop Date + 7 days

¹ Date is the start date of the assessment/event.

Table 14 Study Period Definitions

Study Intervention Period	Definition
GSK3228836 Treatment Period	For Assessments – All Analysis Timepoints within : WK 1 DAY 1 to a day prior PEGIFN ELIGIBILITY WK 1 DAY 1* For Events – Study Treatment Start Date ≤ Date ¹ < GSK836 Last Treatment Date + 7 days
PegIFN Eligibility Period	For Assessments – All Analysis Timepoints within : 1) PEGIFN ELIGIBILITY WK 1 DAY 1 to a day prior PEGIFN DOSING WK 1 DAY 1* and 2) PEGIFN ASSESSMENT WK 14 to a day prior OT-W1 OT-DAY 1*

Study Intervention Period	Definition
	For Events – $GSK836 \text{ Last Treatment Date} + 7 \text{ days} \leq \text{Date}^1 < \text{PegIFN Treatment Start Date}$ *if subject withdrew or never received PegIFN dosing before PegIFN Dosing Visit then end of period would be 'Last PegIFN Assessment Week Stop Date + 7 days'
PegIFN Treatment Period	For Assessments – All Analysis Timepoints within : PEGIFN DOSING WK 1 DAY 1 to a day prior OT-W1 OT-DAY 1* For Events – $\text{PegIFN Treatment Start Date} \leq \text{Date}^1 < \text{PegIFN Treatment Stop Date} + 7 \text{ days}$
Follow-up Period	For Assessments – All Analysis Timepoints within : OT-W1 OT-DAY 1* onwards For Events – If subject never received PegIFN dosing and did not discontinue on-treatment - $\text{Date}1 \geq \text{Last PegIFN Assessment Week Stop Date} + 7 \text{ days}$ Else $\text{Date}1 \geq \text{Last Treatment Stop Date} + 7 \text{ days}$

¹ Date is the start date of the assessment/event.

* If a subject withdrew early or skipped period(s), consider start of next period analysis timepoint. If analysis timepoint is not collected, use corresponding planned start visit day in Section 6.2.8.

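### GSK3228836-period AE and worst-grade laboratory tables set crude percentages over 168 days (Arm 1) beside 84 days (Arm 2), with no table for that period cut to common time

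*SAP*

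**What the plan says.** Both arms receive the same weekly GSK3228836 dose and the same two loading doses, for 24 weeks in Arm 1 and 12 weeks in Arm 2 (SAP 1.2). SAP 6.1.5 gives the dose counts: "The planned number of doses are 26 or 14 for Arm 1 & Arm 2 respectively".

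SAP 4.5.2 lists sixteen AE summaries by arm over the whole study, then adds that these "will also be presented separately for events occurring during treatment with GSK3228836 and PegIFN, overall and by treatment arm within each treatment period". The unit is the participant unless stated otherwise; the SAE and non-serious AE occurrence tables also count events. SAP 4.1.1 reports categorical data as counts and percentages, and Protocol 9.4.4 tabulates proportions with AEs. SAP 4.5.3.1 says the shift, worst-case and maximum-grade laboratory summaries "will also be presented for treatment with GSK3228836 and PegIFN separately, by treatment arm and in total within each treatment period".

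SAP 4.5.2 gives the GSK3228836 AE period no explicit end. SAP Table 14 (6.2.2) supplies one: onset must fall before "GSK836 Last Treatment Date + 7 days".

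On exposure, SAP 4.5.1 says: "Number of days of exposure to study drug will be calculated separately for GSK3228836 and PegIFN". That duration is only described and is never a denominator. Neither document specifies a person-time rate, a time-to-first-AE analysis or a common 12-week cut. AE incidence rates are mentioned only for the before-and-after pandemic summaries (SAP 4.5.2.3), without a person-time definition and not by arm.

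**The concern.** Treatment is identical in the two arms through Week 12. Arm 1's expected percentage for the GSK3228836 period therefore cannot be below Arm 2's, and is higher if any first event, or any worse laboratory grade, occurs in Weeks 13-24. A reader who sees a gap between the columns cannot tell whether the second 12 weeks carry more risk per week, the same risk, or less. The overall column pools a 12-week risk with a 24-week risk.

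SAP Section 2 says the study should inform the choice of Phase III regimen, and the regimens differ in GSK3228836 duration. How safety changes with duration is therefore a natural question for these tables. Late risk cannot be assumed away: Protocol 2.3.1 and 8.3.7.3 describe a gradual platelet decline as the more common form of thrombocytopenia in this drug class.

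**Working it through.** **1. The plan's own figure.** Weekly doses plus two loading doses: 24 + 2 = 26 and 12 + 2 = 14. Both match SAP 6.1.5.

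**2. Window length.** The last scheduled doses are on Day 162 (Protocol Table 2) and Day 78 (Protocol Table 3).
- Events (SAP Table 14, before last dose + 7 days): 162 + 7 - 1 = 168 days; 78 + 7 - 1 = 84 days.
- Assessments (to the day before PegIFN Eligibility Week 1, target days from SAP Table 19): 1 + 7×24 - 1 = 168; 1 + 7×12 - 1 = 84.

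**3. Scheduled post-baseline haematology draws**, weekly from Day 8: (162 - 8)/7 + 1 = 23; (78 - 8)/7 + 1 = 11.

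**4. Effect on a crude percentage.** The documents give no AE risk, so the 12-week risk P12 is an assumption, shown over a range. If the hazard in Weeks 13-24 is a fraction f of that in Weeks 1-12, then P24 = 1 - (1 - P12)^(1+f).

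| Arm 2, P12 | Arm 1, f = 1 | Arm 1, f = 0.5 | Arm 1, f = 0 |
|---|---|---|---|
| 10% | 19.0% | 14.6% | 10% |
| 20% | 36.0% | 28.4% | 20% |
| 30% | 51.0% | 41.4% | 30% |
| 50% | 75.0% | 64.6% | 50% |

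With 50 per arm and f = 1, Arm 1 shows the higher count with probability 0.88 at P12 = 10% and 0.98 at P12 = 30%, although the weekly risk is the same.

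**5. Does a Days 1-84 cut remove the gap?** Yes. Treatment is the same over those days, so the expected percentages are equal whatever the hazard shape.

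**6. Does a person-time rate remove it?** Only with the right denominator and a constant hazard. Take P12 = 30%.
- Weekly hazard h = -ln(0.70)/12 = 0.0297.
- Time at risk, censored at the first event: Arm 1 0.51/0.02972 = 17.16 weeks, Arm 2 0.30/0.02972 = 10.09 weeks. Both arms give 2.97 first events per 100 participant-weeks.
- SAP 4.5.1 duration (last minus first injection + 1): 162 and 78 days. Then 0.51/162 = 0.00315 and 0.30/78 = 0.00385, a ratio of 0.82. Equal weekly risk would make Arm 1 look safer.
- No first events after Week 12 (f = 0), time at risk correctly counted: Arm 1 has 10.09 + 0.70×12 = 18.49 weeks, so 100×0.30/18.49 = 1.62 against 2.97. Even a correct rate then understates Arm 1.

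**The case against.** The strongest reply is that duration is the randomised contrast. Higher cumulative incidence over a 24-week course is a real property of that regimen and is relevant to choosing between regimens. This stands. A reader might infer that the tables are false, or make Arm 1 look less safe purely as an artefact. The documents do not support that: the percentages are correct for what they measure, and the unequal lengths are visible in the exposure tables and SAP Table 14.

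A reader might also infer that no safety table compares the arms over similar time. That is wrong. The main AE summaries cover 72 planned weeks in both arms (24 + 24 + 24 and 12 + 24 + 36, Protocol 1.1), and treatment-emergent status has no end date. By-visit laboratory summaries allow a matched reading through Week 12. The whole-study laboratory shift tables combine on- and off-treatment time, although scheduled haematology in Arm 2 stops at Off-Treatment Week 24. None of these gives AE percentages or worst grades for the GSK3228836 period over common time.

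Nor does the point extend to a planned imbalance in the PegIFN period. Protocol 4.1 sets the same PegIFN duration and delay rules for both arms.

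Finally, safety is an exploratory objective, no formal testing is planned, the between-arm comparison is defined on virologic response, and some table content is left to the Output and Programming Specifications, which are not among the documents. All of this limits the weight of the point but does not supply the missing table.

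**Conclusion.** The point holds as a gap in presentation. For the GSK3228836 period, neither document separates risk per week from length of observation, and the planned windows differ by a factor of two.

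The size is uncertain. At a 12-week risk of 30%, the gap runs from 0 points (no first events after Week 12) through 11 (hazard halved) to 21 (constant hazard). These figures assume planned dosing and a risk level that the documents do not state. The 23 versus 11 draws show unequal opportunity to record a high grade. Turning them into a probability would need a per-sample risk that the documents do not give, and would have to treat repeated draws from one person as independent.

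The equal expectation in Days 1-84 rests on randomisation and identical treatment. It also assumes that knowing the arm, in this open-label study, does not change early reporting or dosing.

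**What to change.** Keep the crude by-period tables. In SAP 4.5.2 and 4.5.3.1, add for the GSK3228836 period a Days 1-84 table for both arms, with Days 85-168 shown separately for Arm 1. Do this for the AE overview, drug-related AEs, AEs of special interest (which SAP 4.5.2.1 does not itself split by period) and maximum-grade laboratory outputs. Define the cut as the SAP Table 14 window truncated at Day 84, and base between-arm statements about weekly risk on it.

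If exposure-adjusted first-event rates are also shown, define the denominator as time at risk within the Table 14 window (to last dose + 7 days), censored at the first event. Do not use the SAP 4.5.1 duration, and add a note that the rate assumes a constant hazard.

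No new data are needed. The cost is SAP wording and a modestly longer table package.
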